### 1. LIST OF ABBREVIATIONS

ΑE Adverse Event AR **Adverse Reaction** ASR **Annual Safety Report** CI Chief Investigator **CRF** Case Report Form **GCP** Good Clinical Practice **HRA** Health Research Authority **ICF** Informed Consent Form **ICT** Intercostal Tube

ICT Intercostal Tube
ISF Investigator Site File
MPE Malignant Pleural Effusion
PI Principal Investigator

PIS Participant Information Sheet
RCT Randomised Control Trial
REC Research Ethics Committee

PSP Primary Spontaneous Pneumothorax

SAR Serious Adverse Reaction
SAE Serious Adverse Event
SOG Safety Oversight Group

SOP Standard Operating Procedure
SSA Site Specific Assessment
TMG Trial Management Group
TSI Trial Specific Instruction
TSC Trial Steering Committee

UACDR Unintentional/Accidental Chest Drain Displacement

Rate

VAS Visual Analogue Score

# 3. STUDY SYNOPSIS

Full study title:	A randomised, controlled trial of the use of a dedicated ballooned intercostal drain			
Short study title:	BASIC			
Chief Investigator:	[name]			
Medical condition/disease under investigation:	Pleural disease requiring intercostal tube (ICT) drainage, including primary spontaneous pneumothorax (PSP), secondary pneumothorax, malignant pleural effusion (MPE), and non-malignant pleural effusion.			
Study duration:	18 months			
Clinical phase:	III			
Device Name:	Ballooned intercostal drain			
Manufacturer Name:	Rocket Medical			
Principal intended use:	Drainage of the pleural cavity			
Primary Objective:	To compare the unintentional / accidental chest drain displacement rate (UACDR) between standard care and a balloon intercostal drain of the same size.			
Secondary Objective:	
 
To assess the difference in patient reported pain scores, using a visual analogue scale
 
To assess the frequency of complications such as balloon rupture or drain blockage and any other complications (such as surgical emphysema, nerve damage, intercostal injuries, etc).
 
To assess difference in the length of hospital stay in both arms.
 
To assess the total number of subsequent pleural procedures (including surgical procedures) in the 30 days after drain removal.
 
To assess the number of days which the patient has any chest drain in situ in the 30 days after drain removal.
 
Assess the number of radiological investigations performed due to issues with any chest drain in situ during the patient's hospital admission.
 
To record the consequences of drain displacement such as failure to complete treatment, delayed discharge the need for subsequent pleural procedures or the need for further medical or surgical care.
 
			
Study population:	Patients requiring intercostal tube drainage of the pleural cavity.			
Methodology:	Randomised controlled trial			
Eligibility criteria:	Inclusion criteria:  1. Age 18 years or over  2. Able to give written informed consent			

3. Requiring intercostal tube drainage for clinical reasons

### Exclusion criteria:

- 1. Inability to provide written informed consent
- 2. Requiring a large bore drain according to local PI or delegated person's clinical judgement.
- 3. Frank haemothorax (requiring a large bore chest drain in view of the local PI or delegated person)
- 4. Pleural space (known prior to intervention) to be too small to place either standard or interventional drain according to local PI or delegated person.
- 5. Drain planned to be in situ for less than 24 hours.
- 6. Any contraindication to chest drain insertion (such as uncorrected clotting abnormality)
- 7. Any patient in acute pain or with an emergency presentation where consideration of the study would inappropriately delay patient care.

### **Study treatment:**

This trial aims to test the benefits of using a dedicated ballooned intercostal drain in patients requiring in-patient drainage of the pleural cavity.

### 4. INTRODUCTION

### 4.1 BACKGROUND

Intercostal tube drainage of pleural air or fluid is an essential tool in the management of respiratory patients. A common complication of drain insertion is accidental removal of the drain, usually as a result of inadequate securing techniques, with rates of up to 21% quoted in the literature for drains inserted for any condition . This study only enrolled patients with malignant pleural effusions so this rate may be higher than in patients with a wider selection of pathologies. The 2015 British Thoracic Society Audit of Pleural Procedures found a 9.2% drain fall out rate, but this was with a range of drain sizes (3). Drain displacement often results in the need for further pleural procedures (including drain re-siting), with associated additional risk to the patient and an increase in health care costs. One suggested method to reduce premature drain removal is to use intercostal drains with ballooned tips, much like Foley bladder catheters. These would provide a relatively atraumatic physical obstruction to the thoracostomy site, whilst being easy to use as stitching or extensive taping may not be required. There is published evidence for the use of non-dedicated ballooned drainage devices for the removal of pleural fluid (5), and data from a pilot study has demonstrated the safety and feasibility of a dedicated ballooned intercostal tube (being prepared for publication). Pain can be a significant issue with intercostal tubes, and occasionally warrants drain removal. The potential reduction in stitching and taping required to ensure the drain remains in the pleural space may reduce the overall discomfort of intercostal tube drainage.

We propose a randomised, controlled trial of a dedicated ballooned intercostal drain (the 'interventional drain') to investigate whether a reduction in accidental early

drain removal can be achieved. Pain scores will also be assessed during this trial to ensure that pleural irritation is not prohibitive, and a cost-effectiveness analysis undertaken.

# 4.2 PRE-CLINICAL DATA/CLINICAL DATA

Data from a pilot study performed at King's Mill Hospital, Sutton-in-Ashfield, demonstrated a fall-out rate of 5% when the interventional drain was used however in this one patient, it is unclear if the balloon was fully inflated within the pleural space (paper being prepared for publication). This compares favourably with rates in the literature when a standard non-ballooned drain is used.

# 4.3 STUDY RATIONALE AND RISK/BENEFIT ANALYSIS

The use of a ballooned ICT has the potential to reduce the accidental fall-out rate, improving the care of patients with pleural disease. Potential risks include increased pain, tissues necrosis and traumatic removal of the ICT and balloon, although none of this occurred using the interventional drain in a pilot study of 20 patients. Pain from pleural irritation did not seem to be an additional problem in that small study.

### 4.4 MANAGEMENT OF POTENTIAL STUDY RISKS

No specific risks related to this study have been identified, although the potential for pleural irritation, incorrect positioning at the time of balloon inflation and tissue necrosis still remains. The patient pathway is identical to usual clinical care, and the interventional drain is CE marked and available for use in clinical practice.

The investigators are not aware of any reported problems or excess adverse events from the use of the interventional drain, and the CI has used the interventional drain without incident.

### 5. STUDY OBJECTIVES

### 5.1 PRIMARY OBJECTIVE

To compare the unintentional / accidental chest drain displacement rate (UACDR) between standard care and a balloon intercostal drain of the same size.

Before a decision is made clinically to remove / reposition the drain, the chest drain:

- Falls out of the pleural cavity completely
- Is displaced such that side drainage holes are clinically no longer in the pleural cavity (for example, flushes resulting in water on the skin / dressings), as judged by the local PI or delegated person.
- Is withdrawn any amount such that the displacement stopped the drain from functioning adequately.
- Is withdrawn by a significant amount according to the local PI or delegated person

• Is confirmed to be displaced by any radiological investigation such as chest X-ray, CT or ultrasound.

Clinical decisions to reposition drains / withdraw drains when treatment is completed will be according to agreed upon trial specific instruction, and documented on the CRFs.

# **5.2 SECONDARY OBJECTIVES**

- 1. To assess the difference in patient reported pain scores, using a visual analogue scale
- 2. To assess the frequency of complications such as balloon rupture or drain blockage and any other complications (such as surgical emphysema, nerve damage, intercostal injuries, etc).
- 3. To assess difference in the length of hospital stay in both arms.
- 4. To assess the total number of subsequent pleural procedures (including surgical procedures) in the 30 days after drain removal.
- 5. To assess the number of days which the patient has any chest drain in situ in the 30 days after drain removal.
- 6. Assess the number of radiological investigations performed due to issues with any chest drain in situ during the patient's hospital admission.
- 7. To record the consequences of drain displacement such as failure to complete treatment, delayed discharge the need for subsequent pleural procedures or the need for further medical or surgical care.

### 6. DESIGN

### 6.1 OVERALL DESIGN

This is a prospective, randomised, interventional clinical study to compare the rate of unintentional / accidental chest drain displacement rate (UACDR) between standard care and a ballooned intercostal tube. Patients undergoing ICT of either pleural effusion or pneumothorax as an in-patient as deemed necessary by the managing physician will be randomised on a 1:1 basis to undergo intercostal tube drainage with either a standard intercostal drain or the interventional drain.

Randomisation will occur via web-based programme and occur with minimisation for the following:

- Recruitment Centre
- Primary indication:
  - Pneumothorax
  - o MPE
  - Infection
  - Other

# **6.2 STUDY INTERVENTION AND RATIONALE**

### 6.2.1 Control arm

Subjects randomised to the control arm will have a standard Seldinger-type non-ballooned intercostal drain inserted at the earliest opportunity as per standard hospital protocols using local anaesthetic, ultrasound guidance (where appropriate) and conscious sedation (where appropriate). Details of the procedure will be recorded on the CRFs, including use of imaging and level of operator. The drain will be 12F drain as this is reflective of clinical practice. The drain size of the control arm will be the same as the size of the trial drain.

The standard drain will aim to be inserted to match the depth of insertion needed for the interventional drain (as per the trial specific instructions). It must also be stitched in place (single standard chest drain holding suture) and secured using bespoke drain holding dressing which will be standardized across the entire study.

All other aspects of their treatment will be identical to usual clinical care, including chest drain checks and fluid drainage strategies, with trial specific instructions available to all sites for each disease area.

[figure not shown]
### 6.2.2 Interventional arm

Subjects randomised to the treatment arm will have the interventional drain inserted at the earliest opportunity as per standard hospital protocols using local anaesthetic, ultrasound guidance (where appropriate) and conscious sedation (where appropriate). Details of the procedure will be recorded on the CRFs, including use of imaging and level of operator.

The drain will be secured using bespoke drain holding dressings which will be standardized across the entire study and the same as for the standard drains. All other aspects of treatment will be identical to usual clinical care, including chest drain checks and fluid drainage strategies, with trial specific protocols available to all sites for each disease area. The operator will be permitted to use a holding suture at their discretion in the interventional arm.

Should any drain in the study become displaced and required re-siting, a standard non-ballooned intercostal drain will be inserted, with size determined by clinical need as assessed by the clinical team. The timing of further drain insertion and drainage time will be recorded (on the discharge CRF).

### 6.3 SCHEMATIC OF TRIAL DESIGN

### 7. ELIGIBILITY CRITERIA

### 7.1 INCLUSION CRITERIA

- 1. Patients aged 18 years or over
- 2. Patients able to give written informed consent
- 3. Patients requiring intercostal tube drainage for clinical reasons

Examples of clinical reasons include:

- a. Drainage of malignant pleural effusion (with or without a view to pleurodesis)
- b. Drainage of pneumothorax (primary or secondary)
- c. Drainage of pleural infection (prior to any surgical intervention)
- d. Drainage of any effusion not in the above diagnostic categories

The most likely or suspected clinical diagnosis should be recorded for randomisation to allow for appropriate minimisation but a final diagnosis will be recorded on the 30 day CRF to allow for more accurate data capture.

A number of conditions are to be included in this pragmatic study of drain management in order to ensure external validity of any trial result, and to provide a wide base for recruitment. In call cases, **it is a requirement that the drain is clinically intended to remain in situ for at least 24 hours** (but a subsequent decision to remove within 24 hours, due to clinical reasons, is acceptable). The requirement above is to ensure that patients being treated for "short term" drainage are NOT included in this study.

### 7.2 EXCLUSION CRITERIA

- 1. Inability to provide written informed consent
- 2. Requiring a large bore drain according to local PI or delegated person's clinical judgement.
- 3. Frank haemothorax (requiring a large bore chest drain in view of the local PI or delegated person)
- 4. Pleural space (known prior to intervention) to be too small to place either standard or interventional drain according to local PI or delegated person.
- 5. Drain planned to be in situ for less than 24 hours.
- 6. Any contraindication to chest drain insertion (such as uncorrected clotting abnormality)
- 7. Any patient in acute pain or with an emergency presentation where consideration of the study would inappropriately delay patient care.

Haemothorax is defined as a pleural fluid haemoglobin of greater than half of the serum haemoglobin value.

If a participant is found to have a frank haemothorax or the pleural space is not big

enough to insert adrain, during or after the procedure, the patient does not need to be withdrawn and the CRFs should be completed as fully as possible rather than submitting a protocol deviation.

# 7.3 DISCONTINUATION/WITHDRAWAL OF PARTICIPANTS AND STOPPING RULES

Patients are free to withdraw their consent to participate in the trial at any time. Drainage of the pleural cavity represents usual clinical care, and is not trial-specific, and therefore any drain inserted would only be removed for clinical reasons, unless specifically requested by the patient after thorough discussion with the team responsible for their usual clinical care. If a patient does withdraw their consent to participate, they can request one of the three methods below.

*No further contact* – means that the research team no longer contacts the patient directly, but still has their permission to use information, samples and to obtain further information from health records.

*No further access* – means that the research team no longer contacts the patient or obtains information from their health records, but still has permission to use the information and samples already collected.

*No further use* — means that the research team no longer contacts the patient or obtains further information, aims to destroy all samples already collected (though tracing previously distributed samples may not always be possible), does not use either data or samples for further analyses, but is not able to remove data from analyses already carried out. Data already entered on to the database cannot be deleted, but will be excluded from analysis.

The reason for withdrawal, if known, will be recorded in the CRF. If the participant is withdrawn due to an adverse event, the investigator will arrange for visits or telephone calls to collect follow-up information on the adverse event until the adverse event has resolved or stabilised.

They will still receive the safety follow-up telephone call at 1 month (see section 10.4) unless they expressly request for this not to happen.

If a participant's is randomised and it becomes apparent a chest drain is no longer required the participant should be withdrawn from the study. However if an attempt is made at inserting a chest drain and it fails the participant should remain in the study.

The investigators reserve the right to postpone recruitment or to terminate the trial early if new information comes to light that renders the trial futile (for example new

clinical data), or there is an apparent safety issue with the interventional drain or any other aspect of the study.

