### 14.STATISTICAL DESIGN

#### 14.1 SAMPLE SIZE AND RECRUITMENT

Based on data from previous studies of drain fall-out rates with standard ICTs and data from the pilot study of ballooned drains, 66 recruited subjects will be required in each arm of the trial on the basis of the following assumptions:

Binary data (drain displaced; drain not displaced)

Power: 0.8

Level of significance: 0.05 Fall-out rate in pilot study: 5%

Fall-out rate in previous studies: 21%

Estimated sample size calculation: 66 in each arm

Calculation based on the formula:

$$n = f(a/2, \beta) \times [p_1 \times (100 - p_1) + p_2 \times (100 - p_2)] / (p_2 - p_1)^2$$

where p1 and p2 are the percent 'success' in the control and experimental group respectively and  $f(\alpha, \beta) = [\Phi^{-1}(\alpha) + \Phi^{-1}(\beta)]^2$ .  $\Phi^{-1}$  is the cumulative distribution function of a standardised normal deviate.

Allowing for a  $\sim$ 2% withdrawal rate (which is realistic as this is a short term study only), the estimated combined sample size for the study is 136 subjects.

It is estimated that recruitment will take up to 18 months, aiming for approximately 1 patient per site per month.

At 50% recruitment the assumption that 21% of non-balloon drains would displace was reviewed by the TSC. However after reviewing the data this was found to be 12%. Since this was lower than expected the trial was likely to be underpowered, and therefore the sample size was increased to allow the same relative reduction in displacement to be detected. The initial sample size calculation aimed to detect a reduction from 21% to 5%, a relative reduction of 21-5/21 = 76%. To detect the same relative reduction the displacement rate in the balloon arm would be assumed to be 12\*(1-0.76) = 2.88%. This was rounded to 3% (i.e. more conservative and therefore a slightly higher sample size). The new sample size required to detect a reduction in displacement rates from 12% to 3%, and allowing for a 2% withdrawal rate, was 267.

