# 14.3.1 Primary endpoint analysis

The primary end point for the trial is difference in the UACDR between control and interventional arms and will be analysed as part of a detailed statistical analysis plan, to include time to event analysis as above. The analysis will be performed on an intention to treat basis.

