### 14.5 OTHER STATISTICAL CONSIDERATIONS

Intention to treat will be undertaken in order to account for patients who are randomised but then do not have an intercostal tube sited for any reason. The reason for non-insertion will be documented in the clinical notes.

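### Section 7.3 withdraws randomised patients who turn out not to need a drain, in conflict with the intention-to-treat statement in section 14.5

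*Protocol*

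**What the plan says.** Protocol section 7.3 instructs sites that if, once a participant has been randomised, "it becomes apparent a chest drain is no longer required the participant should be withdrawn from the study". Its next sentence treats failed attempts the other way: "if an attempt is made at inserting a chest drain and it fails the participant should remain in the study". Section 7.2 is similarly inclusive. A patient whose pleural space proves too small at or after the procedure need not be withdrawn, and the CRFs are completed as far as possible.

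Section 14.5 gives the purpose of intention to treat as accounting for "patients who are randomised but then do not have an intercostal tube sited for any reason". It adds "The reason for non-insertion will be documented in the clinical notes" and states no exclusion. On the primary endpoint, section 14.3.1 says "The analysis will be performed on an intention to treat basis".

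Section 7.3 also describes withdrawal of consent at three levels, of which only the strictest takes data out of the analysis, and withdrawal because of an adverse event, with follow-up of that event. Sections 10.4 and 14.2.2 count length of stay from insertion of the study drain, and further procedures and the 30-day contact from its removal.

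**The concern.** A randomised patient who improves, or is reassessed, before insertion is covered by two statements. Section 7.3 takes that patient out of the study; section 14.5 names patients without a tube, whatever the cause, as those whom intention to treat is meant to cover. The protocol nowhere says that patients withdrawn under 7.3 are still analysed, or how their outcome is set.

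The judgement that a drain is no longer needed comes after allocation. No blinding is described, the two drains look different, and the holding suture is mandatory in one arm and optional in the other (sections 6.2.1 and 6.2.2). Staff can therefore know the allocation when they decide. If these patients then drop out of the analysis, the comparison is open to selection that could differ by arm, which intention to treat exists to prevent.

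A site that withdraws a patient may also stop completing forms. Length of stay and later procedures would then be at risk for that patient. This is an instruction on conduct, so an analysis plan written later could define the analysis set but could not recover data that were not collected.

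**Working it through.** **1. The statements side by side**

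| Randomised patient | Section 7.3 or 7.2 | Section 14.5 |
|---|---|---|
| Insertion attempted and failed | Stays in the study | Covered |
| Space found too small at or after the procedure | Need not be withdrawn | Covered if no tube is sited |
| Drain no longer required | Withdrawn from the study | Covered |

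Only the last row conflicts.

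**2. The plan's own figure.** Inputs from section 14.1: 12% and 3% displaced, two-sided 5%, power 80%, 2% withdrawal. With the protocol's formula:

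n per arm = (1.960 + 0.842)² × [0.12 × 0.88 + 0.03 × 0.97] / 0.09² = 7.849 × 0.1347 / 0.0081 = 130.5, so 131.

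Total = 2 × 130.52 / 0.98 = 266.4, so 267. This matches the stated figure.

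**3. Effect on the primary difference.** The protocol gives no rate for drains no longer required, so I assume 1% to 5% of 267, which is 2.7 to 13.4, or about 3 to 13 patients. Expected events are 0.12 × 131 = 15.7 and 0.03 × 131 = 3.9, about 16 and 4. A patient without a drain has no displacement, so removal changes only denominators. The extreme case takes all removals from one arm:

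| Removed | Control | Balloon | Difference (points) |
|---|---|---|---|
| None | 16/131 = 12.2% | 4/131 = 3.1% | 9.2 |
| 3, all balloon | 16/131 = 12.2% | 4/128 = 3.1% | 9.1 |
| 3, all control | 16/128 = 12.5% | 4/131 = 3.1% | 9.4 |
| 13, all balloon | 16/131 = 12.2% | 4/118 = 3.4% | 8.8 |
| 13, all control | 16/118 = 13.6% | 4/131 = 3.1% | 10.5 |

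**4. Effect on power.** Normal approximation with pooled variance under the null:

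power = Φ{[√n × (p1 − p2) − 1.960 × √(2p̄(1 − p̄))] / √(p1(1 − p1) + p2(1 − p2))}, where p̄ is the mean of p1 and p2.

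With n = 267/2 = 133.5 and no loss: (1.040 − 0.730) / 0.367 = 0.844, so power is 80.1%. Let a share d in each arm never receive a drain. Keeping them as non-events multiplies both rates by (1 − d); removing them multiplies n by (1 − d).

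| d | Kept as non-events | Removed |
|---|---|---|
| 2% | 79.2% | 79.3% |
| 5% | 77.8% | 78.0% |
| 10% | 75.4% | 75.8% |

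Keeping or removing changes power by 0.1 to 0.4 points. The issue is who is in the analysis, not how many.

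**5. Secondary outcomes.** A patient with no drain has neither an insertion nor a removal date. Length of stay and the 30-day outcomes therefore have no defined start for this patient, even if follow-up continues.

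**The case against.** The strongest reply is that 7.3 governs conduct and 14.3.1 and 14.5 govern analysis, so a patient can be withdrawn from procedures and still be analysed as allocated. A reader might infer that the two rules cannot both be followed. The text does not go that far: withdrawal is not stated to mean exclusion, and only the strictest consent option removes data from the analysis. This stands, but it does not settle the matter, because 7.3 sets withdrawal against remaining in the study and no section says these patients are analysed.

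A reader might also infer that the data for the intention-to-treat analysis would not exist. That is too strong. The primary outcome follows from non-insertion, the reason for which must be documented. Section 7.3 mentions a 1-month call for withdrawn participants, although it may refer only to adverse-event withdrawals. Section 10.4 allows the 30-day form to be completed from the notes when contact fails. What remains is a risk to secondary data.

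Nor do the documents show that the exclusion would depend on arm. The drains are the same size, the indications are the same, and nothing says that the need for drainage varies with allocation. It could differ by arm; no more can be said.

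Finally, one might argue that failed insertions, which stay in, are scored as successes. That rests on reading a data-type line in the sample-size section as a scoring rule. How they are scored can be left to the analysis plan, so it forms no part of this point.

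**Conclusion.** The conflict between 7.3 and 14.5 is real and should be fixed. The protocol leaves it unclear whether randomised patients who no longer need a drain belong to the primary analysis set, and it allows an unblinded decision after randomisation to determine this.

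The likely numerical effect is small. Under the assumed 5% and the extreme of all 13 removals from one arm, the difference moves from about 9.2 points to 8.8 or 10.5; with 3 removals it moves to 9.1 or 9.4. These figures rest on the revised planning rates, on an affected share that the protocol does not give, and on counting a patient without a drain as not displaced. It would be wrong to set the number of affected patients against the number of expected events as if they could swamp the result: none of them is an event. The sample size of 267 is reproduced and is not in error.

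**What to change.** Reconcile the sections by changing the sentence in 7.3. A randomised patient whose drain is no longer required should:

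- stay in the study and in the intention-to-treat set as allocated;
- be counted as no displacement;
- have outcome data collected from the notes or the 30-day contact, with time counted from randomisation.

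Leave the consent and adverse-event withdrawal routes in 7.3 as they are. A cross-reference in 14.5 would help.

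The cost is one or two sentences, a note to sites and follow-up of a few patients. No change to the sample size is needed.
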